### **7.2 Number of Patients**

It is expected that approximately 30 evaluable subjects (approximately 22 subjects with HL and approximately 8 subjects with sALCL) will be enrolled in this study. The justification for the sample size is described in Section [14.3](#).

### **7.3 Duration of Study**

The screening period will be up to 4 weeks, and the treatment period will be up to 16 cycles (approximately 12 months). Patients will have safety follow-up assessments through 30 days after the last dose of brentuximab vedotin. All patients who discontinue brentuximab vedotin for any

reason other than withdrawal of full consent will undergo a long-term follow-up every 12 weeks after the safety follow-up assessments. Patients will be followed until all patients have had the opportunity to be followed for 18 months after EOT. The study will be closed when all patients enrolled have completed the required follow-up. It is expected that the study will last approximately 3.5 years.

## **8.0 STUDY POPULATION**

### **8.1 Inclusion Criteria**

Each patient must meet all of the following inclusion criteria to be enrolled in the study:

1. Male or female Chinese patients aged 18 years or older at the time of informed consent.
2. Patients must have histologically confirmed CD30+ HL or sALCL. Immunohistochemistry or flow cytometry may be performed on either original diagnostic biopsy material or biopsy of relapsed disease, and pathology reports of CD30+ or their copies should be retained at the site.
3. Patients with CD30+ HL or sALCL who have relapsed from or are refractory to previous treatments.
4. Fluorodeoxyglucose (FDG)-PET positive and measurable disease of at least 1.5 cm in the longest diameter by CT, as assessed by the site.
5. Patients must have an Eastern Cooperative Oncology Group (ECOG) performance status of 0 or 1.
6. Voluntary written consent must be given before performance of any study-related procedure not part of standard medical care, with the understanding that consent may be withdrawn by the patient at any time without prejudice to future medical care.
7. Female patients who:
  - Are postmenopausal for at least 1 year before the screening visit, OR
  - Are surgically sterile, OR
  - If they are of childbearing potential, agree to practice 2 effective methods of contraception, at the same time, from the time of signing the informed consent through 6 months after the last dose of study drug.

Male patients, even if surgically sterilized (ie, status postvasectomy), who:

- Agree to practice effective barrier contraception during the entire study treatment period and through 6 months after the last dose of study drug.

8. Suitable venous access for the study-required blood sampling, including PK sampling.
9. Patients must have the following required screening laboratory data. Patients must not have received recombinant granulocyte-colony stimulating factor (G-CSF) or platelet transfusion within 1 week before the screening hematology assessment.
  - Absolute neutrophil count  $\geq 1500/\mu\text{L}$ .
  - Platelet count  $\geq 75,000/\mu\text{L}$ .
  - Serum bilirubin level  $\leq 1.5$  times the upper limit of the normal range (ULN).
  - Serum creatinine level  $\leq 1.5$  times the ULN.

- Alanine aminotransferase (ALT) and aspartate aminotransferase (AST)  $\leq 2.5$  times the ULN.
- 10. Survival for 3 or more months must be expected.

## **8.2 Exclusion Criteria**

Patients meeting any of the following exclusion criteria are not to be enrolled in the study:

1. Patients with current diagnosis of primary cutaneous ALCL (patients with other organ involvement who have transformed to sALCL are eligible).
2. Female patients who are lactating and breast-feeding or have a positive serum pregnancy test during the screening period.
3. Patients with any active viral, bacterial, or fungal infection within 2 weeks before the first dose of brentuximab vedotin.
4. Patients with cardiac failure categorized as Class III or IV according to the New York Heart Association criteria, uncontrolled coronary artery disease or uncontrolled arrhythmia despite of appropriate medical therapy, or a history of myocardial infarction within 6 months before the first dose of brentuximab vedotin.
5. Patients with uncontrolled diabetes mellitus.
6. Peripheral neuropathy  $\geq$ Grade 2 (NCI CTCAE version 4.03) [2].
7. Patients with a history of another malignancy that has not been in remission for at least 3 years. The following are exempt from the 3-year limit:
  - Nonmelanoma skin cancer.
  - Curatively treated localized prostate cancer.
  - Cervical carcinoma in situ.
8. Patients with known cerebral/meningeal disease (HL or any other etiology), including signs or symptoms of PML (see Section 9.6.5).
9. Patients with a positive result in the screening test for human immunodeficiency virus (HIV) antibody.
10. Known hepatitis B virus (HBV) surface antigen seropositive or positive hepatitis C virus (HCV) antibody. Note: patients who have positive HBV core antibody can be enrolled but must have an undetectable HBV viral load.
11. Patients with a history of liver fibrosis or cirrhosis and clinical signs and symptoms indicating liver fibrosis or cirrhosis.
12. Patients who have received auto-SCT within 12 weeks before the first dose of brentuximab vedotin.
13. Patients with history of allo-SCT.

14. Patients who have received treatment for malignancies (including radiation, chemotherapy, and hormone therapy) within 4 weeks before the first dose of brentuximab vedotin and patients who have received treatment for malignancies with biologics (including molecular target drug) or radioisotopic therapy within 12 weeks before the first dose of brentuximab vedotin.
15. Patients who have unresolved toxicity higher than Grade 1 (NCI CTCAE version 4.03) [2] attributed to any prior therapy/procedure (excluding alopecia or non-clinically significant and asymptomatic laboratory abnormalities).
16. Patients who have received systemic corticosteroids at doses greater than the equivalent of 20 mg/day of prednisone within 1 week before the first dose of brentuximab vedotin.
17. Patients who have received other investigational products within 4 weeks before the first dose of brentuximab vedotin.
18. Patients who have received treatment with investigational medical devices within 4 weeks before the first dose of brentuximab vedotin.
19. Patients who have received previous treatment with brentuximab vedotin.
20. Patients with a known hypersensitivity to any excipient contained in the drug formulation.
21. Patients who have any kind of disorder that compromises the ability of the patient to give written informed consent and/or to comply with study procedures.
22. Comorbid systemic illnesses or other severe concurrent disease which, in the judgment of the investigator, would make the patient inappropriate for entry into this study or interfere significantly with the proper assessment of the safety and toxicity of the prescribed regimens.

## **9.0 STUDY DRUG**

### **9.1 Study Drug Administration**

All protocol-specific criteria for administration of study drug must be met and documented before drug administration. Study drug will be administered only to eligible patients under the supervision of the investigator or identified subinvestigator.

Brentuximab vedotin will be administered as an IV infusion over approximately 30 minutes on Day 1 of each 21-day cycle at a dose of 1.8 mg/kg. After Cycle 2, except when it takes longer for the subject to recover from toxicity that is possibly related to brentuximab vedotin after the most recent cycle (refer to Section 9.2), an administration window of -1 to +3 days is allowed. Patients with a tumor response (CR or PR) or SD for whom there are no safety concerns may receive up to 16 cycles of brentuximab vedotin.

Brentuximab vedotin should not be given as a rapid IV dose or bolus injection. Brentuximab vedotin should be given through a dedicated infusion line and should not be mixed with other drug products.

The infusion line should be flushed with saline solution before and after brentuximab vedotin administration to avoid mixing with other drug products.

The dose of brentuximab vedotin will be calculated based on the subject's actual body weight at Baseline, and the calculated brentuximab vedotin dose will be rounded to the nearest whole number. If the subject experiences a  $\geq 10\%$  change in body weight during the study, the dose should be adjusted. Note that if a patient weighs more than 100 kg, the dose for the patient will be calculated assuming the body weight to be 100 kg.

Patients will be monitored at bedside from the start of dosing for the first and second doses of brentuximab vedotin. Premedication to prevent infusion-related reactions may be used before dosing of brentuximab vedotin according to investigator discretion and institutional guidelines. Premedication use is further described in Section 9.6.3. If an infusion-related reaction occurs, continuation of brentuximab vedotin dosing will be based on the severity of the event and at the discretion of the investigator following discussion with the sponsor.

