#### **4.1.5 Known or Potential Risks of Brentuximab Vedotin**

- Brentuximab vedotin treatment causes peripheral neuropathy, both sensory and motor. Brentuximab vedotin-induced peripheral neuropathy is typically cumulative and generally reversible. Monitoring patients for symptoms of neuropathy, such as hypoesthesia, hyperesthesia, paresthesia, discomfort, a burning sensation, and neuropathic pain or weakness, is required. Patients experiencing new or worsening peripheral neuropathy may require brentuximab vedotin dose modifications, including a dose delay (see [Table 9.a](#)).
- Complete blood counts should be monitored before each dose of brentuximab vedotin, and more frequent monitoring should be considered for patients with Grade 3 or 4 neutropenia. Prolonged ( $\geq 1$  week) severe neutropenia can occur. If Grade 3 or 4 neutropenia develops, manage with dose delays, reductions, or discontinuations (see [Table 9.a](#)).
- Infusion-related reactions, including anaphylaxis, have occurred with brentuximab vedotin. Monitoring of patients during infusion is required. If anaphylaxis occurs, the administration of brentuximab vedotin should be immediately and permanently discontinued and appropriate medical therapy administered. Patients who have experienced a prior infusion-related reaction should be premedicated according to institutional guidelines for subsequent infusions. Premedication may include acetaminophen, an antihistamine, and a corticosteroid.

- Any treatment that can decrease immune function may contribute to malignancy and infections; patients are to be monitored for these events during the treatment period and up to and including 30 days after the last dose.
- Stevens-Johnson syndrome (SJS)/toxic epidermal necrolysis (TEN) have been reported with brentuximab vedotin. If SJS/TEN occurs, brentuximab vedotin must be discontinued and the appropriate medical therapy administered.
- Tumor lysis syndrome may occur. Patients with rapidly proliferating tumors and high tumor burden are at risk of tumor lysis syndrome and should be closely monitored. If tumor lysis syndrome occurs, take medically appropriate measures.
- Progressive multifocal leukoencephalopathy (PML) has been reported with brentuximab vedotin use. If PML is suspected, a diagnostic work-up should be performed as described in Section 9.6.5.

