**Table 9.a Criteria for Dose Adjustments and Delays**

Toxicity	Grade 1	Grade 2	Grade 3	Grade 4
Non-hematologic	Continue at the same dose level (1.8 mg/kg).	Continue at the same dose level (1.8 mg/kg), except in the event of Grade 2 neuropathy. For Grade 2 neuropathy, withhold dose until toxicity is $\leq$ Grade 1 or has returned to baseline, then resume treatment at the same dose level (1.8 mg/kg). For the second occurrence of Grade 2 neuropathy, withhold dose until toxicity is $\leq$ Grade 1, then reduce the dose to 1.2 mg/kg and resume treatment after discussion with the sponsor.	The investigator/subinvestigator will make decisions on the appropriateness of brentuximab vedotin treatment in subsequent cycles after discussion with the sponsor. For subjects who are determined to be able to continue treatment with brentuximab vedotin, continue treatment at the same dose level (1.8 mg/kg) or by reducing the dose to 1.2 mg/kg. Confirm that toxicity is $\leq$ Grade 1 or has returned to baseline before continuing treatment (a). For Grade 3 or higher neuropathy, consider discontinuing treatment after discussion with the sponsor.	The investigator/subinvestigator will make decisions on the appropriateness of brentuximab vedotin treatment in subsequent cycles after discussion with the sponsor. For subjects who are determined to be able to continue treatment with brentuximab vedotin, confirm that toxicity is $\leq$ Grade 1 or has returned to baseline, then continue treatment by reducing the dose to 1.2 mg/kg (a).

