### **9.6.3 Infusion-Related Reactions**

Infusion-related reactions may occur during the infusion of brentuximab vedotin. The infusion should be administered at a site properly equipped and staffed to manage an infusion-related reaction, including anaphylaxis should it occur. The patient should be observed for approximately 60 minutes following the first infusion of brentuximab vedotin. During this observation period, the IV line should remain open for at least 1 hour to allow administration of IV drugs if necessary. All supportive measures consistent with optimal patient care will be given throughout the study according to institution standards. Medications for infusion-related reactions, such as epinephrine and antihistamines, should be available for immediate use.

Patients who experience a Grade 1 or 2 infusion-related reaction may receive subsequent brentuximab vedotin infusions with premedication consisting of acetaminophen (650 mg orally) and diphenhydramine (25-50 mg orally or 10-25 mg IV) or according to institutional standards, administered 30 to 60 minutes before each 30-minute brentuximab vedotin infusion.

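### Section 4.1.5 tells sites to stop the drug for anaphylaxis and for SJS/TEN, but Section 9.1 (anaphylaxis) and Table 9.a (both events) leave continuation to judgment with no exception

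*Protocol*

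**What the plan says.** **The stops.** Protocol Section 4.1.5, in the introduction, contains two:

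- Anaphylaxis: "If anaphylaxis occurs, the administration of brentuximab vedotin should be immediately and permanently discontinued".
- SJS/TEN: "If SJS/TEN occurs, brentuximab vedotin must be discontinued and the appropriate medical therapy administered".

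Neither depends on grade, recovery or the investigator's view. The verbs differ: *should* for anaphylaxis, *must* for SJS/TEN. Only the anaphylaxis sentence says the stop is permanent.

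**The dosing rules.** Section 9.1 deals with infusion-related reactions as a class: "continuation of brentuximab vedotin dosing will be based on the severity of the event and at the discretion of the investigator". The sentence goes on to require discussion with the sponsor. Section 9.6.3 covers site readiness, observation and premedication for these reactions.

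Table 9.a, under Section 9.2, handles treatment-related non-hematologic toxicity by grade. At Grades 3 and 4 the investigator decides, after discussion with the sponsor, whether later cycles are appropriate. For patients judged able to go on, and once the toxicity has recovered, the Grade 3 cell allows the same or the reduced dose. The Grade 4 cell ends "then continue treatment by reducing the dose to 1.2 mg/kg (a".

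**The concern.** Section 9 is where the protocol puts its rules for giving, delaying, reducing and withholding the drug. An investigator deciding on the next dose after one of these events would find a judgment to make there, together with the sponsor. In Section 4.1.5 the same investigator would find that the decision has already been made. Neither place refers to the other for these two events.

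Patient safety is at stake, along with consistent conduct across about 7 sites. Two sites could handle the same event differently, each pointing to protocol text, and it would be unclear which had deviated. Section 12.0 provides for no data safety monitoring committee, so reconciliation would depend on the exchange between site and sponsor.

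**Working it through.** No arithmetic applies. The check is to set the passages side by side, one event at a time.

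**Step 1. Does Section 9.1 govern anaphylaxis?** Yes, by the protocol's own classification. Section 4.1.5 says "Infusion-related reactions, including anaphylaxis, have occurred with brentuximab vedotin", and Section 9.6.3 asks for sites equipped "to manage an infusion-related reaction, including anaphylaxis should it occur". Section 9.1 sets one rule for infusion-related reactions and excepts none.

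**Step 2. Does Section 9.1 govern SJS/TEN?** No. Nothing in the protocol classes SJS/TEN as an infusion-related reaction.

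**Step 3. Does Table 9.a govern either event?** Both are non-hematologic, so both fall in that row when treatment-related. The row singles out neuropathy, and its footnote exempts only electrolyte abnormalities. Neither anaphylaxis nor SJS/TEN is excepted. The documents do not say how either event would be graded, so I assume Grade 3 or 4. The lower-grade cells contain no stop for these events either.

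**Step 4. Compare.**

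| Event | Section 4.1.5 | Section 9.1 | Table 9.a, Grade 3–4 non-hematologic | Section 9.6.3 | Section 10.6 |
|---|---|---|---|---|---|
| Anaphylaxis | Stop, immediate and permanent (*should*) | Severity and investigator discretion, with sponsor discussion; no exception | Investigator decision with sponsor discussion; path to continue; no exception | Named; no stop given | Not named; AE listed generically |
| SJS/TEN | Stop (*must*) | Does not apply | Investigator decision with sponsor discussion; path to continue; no exception | Does not apply | Not named; AE listed generically |

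**Step 5. Which cells conflict?** The Section 9.1 and Table 9.a entries do, because they treat continuing as a possible outcome where Section 4.1.5 does not. The other two columns are omissions:

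- Section 9.6.3 gives no stop for anaphylaxis. Its permission is limited: "Patients who experience a Grade 1 or 2 infusion-related reaction may receive subsequent brentuximab vedotin infusions with premedication". It is silent on higher grades.
- Section 10.6 lists reasons for which treatment may be discontinued. AE is among them, so a stop under Section 4.1.5 fits within it.

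**Step 6. Is there a tie-breaker?** No statement of precedence was found. The handling of other risks shows how the link could have been made. Section 4.1.5 refers to Table 9.a for neuropathy and neutropenia, and to Section 9.6.5 for PML, where an absolute stop on confirmed PML is written into Section 9. Anaphylaxis and SJS/TEN have neither a cross-reference nor a counterpart in Section 9.

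**The case against.** The strongest reply is that this is a general rule lacking an exception, not two opposite orders. No passage says that a patient may be re-treated after anaphylaxis or SJS/TEN. Table 9.a does not send every Grade 3 or 4 patient back to treatment: the continuation wording applies only to patients already judged able to continue, and Section 4.1.5 can be read as settling that judgment. Both dosing passages require discussion with the sponsor. SAEs must be reported to the sponsor's pharmacovigilance department within 24 hours (Section 11.2). Section 9.1 reserves up to 16 cycles for patients without safety concerns, Section 7.1 ends treatment at unacceptable toxicity, and investigators must follow the whole protocol (Appendix B), which includes Section 4.1.5.

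Most of this stands, and it makes re-treatment against Section 4.1.5 less likely. It does not remove the conflict. A required discussion about continuing presupposes that continuing is possible, and Section 4.1.5 says it is not. Reading the specific rule as overriding the general one is sensible, but the protocol does not say so, and here the specific rule sits in the background text while the general one sits in the dosing section.

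A reader might infer that the whole operational part of the protocol contradicts Section 4.1.5 for both events. The documents do not support that. Section 9.1 has no bearing on SJS/TEN, Section 9.6.3 is silent rather than contrary, and Section 10.6 is compatible with a stop.

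**Conclusion.** The protocol is inconsistent as written, within narrow limits. For anaphylaxis, the stop in Section 4.1.5 conflicts with the discretionary rule in Section 9.1, and the general non-hematologic row of Table 9.a has no exception. For SJS/TEN, the conflict is with Table 9.a alone.

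The conclusion rests on three readings: anaphylaxis is an infusion-related reaction, as the protocol twice says; both events would be graded 3 or 4 in Table 9.a; and no unstated precedence applies. The Investigator's Brochure and Study Manual were not available and might narrow the gap in practice, but the protocol should agree with itself.

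The consequence is for patient safety and consistent conduct. The documents give no frequency for either event, so the number of patients affected cannot be estimated. No sample size, power, confidence interval or other analysis figure depends on the point. A reader might go further and infer that the safety endpoint is compromised or that sites are told to re-treat; nothing in the documents shows either.

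**What to change.** Reconcile Section 4.1.5 with Section 9.1 and Table 9.a so that each gives the same instruction for anaphylaxis, and Section 4.1.5 with Table 9.a so that both give the same instruction for SJS/TEN. The sponsor decides which clinical rule stands; this review takes no position on it. Whatever is chosen:

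- in Section 9.1, state how anaphylaxis relates to the general rule for infusion-related reactions;
- in Table 9.a, state how the two events relate to the Grade 3 and 4 non-hematologic cells, for example in a footnote beside the existing ones;
- add cross-references between these places and Section 4.1.5, and one from Section 9.6.3, where a reader would look for anaphylaxis;
- settle whether the difference in wording between the two stops in Section 4.1.5 is intended.

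Section 10.6 needs no change for consistency. The cost is a few lines in an amendment, with notice to sites. The SAP, sample size and analyses are untouched.

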### **9.2 Dose Modification Guidelines**

If treatment-related toxicity occurs, intrapatient dose reduction will be allowed to 1.2 mg/kg for each subject depending on the type and severity of the toxicity. If a patient requires further dose reductions, brentuximab vedotin will be permanently discontinued. Table 9.a provides the criteria for dose adjustments and delays for treatment-related toxicity. Toxicity will be evaluated according to the NCI CTCAE, version 4.03 [2].

If a patient fails to meet the criteria for re-treatment cited in Table 9.a, initiation of the next cycle of treatment should be delayed up to 1 week. At the end of that time, the patient should be re-evaluated to determine whether the criteria for re-treatment have been met. The start of the next cycle may be delayed for up to 3 weeks (6 weeks after the most recent dose) if additional time is

required for the patient to recover from treatment-related toxicity experienced during the current cycle. Delays of longer than 3 weeks (after Day 22) are prohibited without approval from the sponsor.

Doses reduced for treatment-related toxicity should generally not be re-escalated; however, intrapatient re-escalation to 1.8 mg/kg may be permitted at the discretion of the investigator after a discussion with the sponsor.

